#### 11.2 Analysis methods

All analyses will proceed using standard analytical techniques including Kaplan-Meier survival curves. Analysis will include tabulation of baseline characteristics of recruited patients. Intention to treat analysis will be used. Baseline characteristics for those patients not completing trial treatment will be tabulated for comparison with treated patients, to ensure the ability to generalise results. Baseline characteristics will include (but are not limited to) demographic data, tumour stage and grade. Categorical data will be reported as a percentage. Numeric data will be reported as median, mean, range and SD.

#### 11.3 **Primary endpoint**

#### Objective Response rate

To assess objective response rate (ORR) of cemiplimab in laBCC patients by independent central review at 6 months. ORR is defined as the proportion of patients having achieved partial or complete remission. This will be assessed for patients with visible tumour(s) only, using the clinical response criteria (see Appendix 2 table 1) according to World Health Organization (WHO) criteria and for patients who have target lesions measurable by both clinical response and radiologically by RECIST1.1, using the composite response criteria (see

Appendix 2 table 2). ORR will be reported with 80% and 95% CI (Confidence Intervals) using the Wilson score interval.

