# 11.1 Sample size calculations

The hedgehog pathway inhibitors (HHIs) have shown an ORR of about 45% in the first line setting. In the ERIVANCE study, the ORR with vismodegib was 42.9% at 9 months follow-up which increased to 47.6% at 21 months follow-up (9). In the BOLT study of sonidegib, the ORR was 47.0% at primary 6 month follow-up, increasing to 56.1% (95% CI: 43.3–68.3) at 18 month follow-up (10). In the second line setting, cemiplimab showed an ORR of 31%, in a recently reported phase 2 study in the 2nd line setting (18), after a median follow-up of 15 months.

Assuming an ORR of cemiplimab to be around 45% at 6-months in the first line setting, this study is powered as a single arm Simon II Stage design. This will be used to differentiate between a poor treatment (success rate of 25%) and a good treatment (success rate 45%) using a nominal significance level alpha = 5% and a power of 80%.

Once 18 patients are recruited, an interim analysis will be performed with the decision rule of progression to Stage II if 6 or more of the 18 patients achieve a response. If ≤5 patients have responded (poor response) or if 15 out of the 18 patients have responded (exceptional response) the trial will be stopped.

Stage II will be the recruitment of a further 19 patients. To account for a potential loss of non-evaluable patients (assuming a 10% drop out rate) the sample size will be inflated to N = 41.

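### Section 11.3 fixes a fixed-sample Wilson interval for the primary ORR of a Simon two-stage trial; the 80% interval loses coverage (75.0% at the design ORR of 45%), while the 95% interval is little affected

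*Protocol*

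**What the plan says.** Section 11.1 of the protocol says that "this study is powered as a single arm Simon II Stage design", with 25% as the poor response rate, 45% as the good one, a 5% significance level and 80% power. The interim rule is "progression to Stage II if 6 or more of the 18 patients achieve a response". If at most five "patients have responded (poor response) or if 15 out of the 18 patients have responded (exceptional response) the trial will be stopped". Otherwise, "Stage II will be the recruitment of a further 19 patients", which makes 37 evaluable patients, inflated to 41 for dropout.

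Section 11.3 defines the primary ORR as the simple proportion with partial or complete remission and fixes its precision statement: "ORR will be reported with 80% and 95% CI (Confidence Intervals) using the Wilson score interval". Sections 11.2 to 11.4 name no estimate or interval that allows for the interim stop. The SAP is not at hand, but the protocol itself names the interval method and both confidence levels, so this is a choice already made and not a detail left open.

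**The concern.** The Wilson interval is derived for a binomial count from a sample whose size does not depend on the data. Here the final size is 18 or 37 according to the stage 1 count. Trials with few early responders are frozen at 18 with a low proportion, and the low start is never diluted by later patients. The observed proportion is then biased over repeated trials, and limits computed as if the size were fixed need not contain the true rate as often as stated.

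The ORR with these two intervals is the only analysis that section 11.3 specifies for the primary endpoint. It will be read against the rates cited in section 11.1: 42.9% to 56.1% for hedgehog inhibitors and 31% for second-line cemiplimab. If the 80% limits are too narrow near 45%, the trial's precision is overstated at its own planning value.

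**Working it through.** **Inputs (section 11.1).** Stage 1 has 18 patients. Stop at 5 or fewer responses, or at 15 or more (the protocol says 15 of 18; read here as at least 15). Otherwise add 19, for 37 in total. The rates are 25% and 45%. The interval (section 11.3) is Wilson at 80% and 95%.

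**1. The design reproduces.** Let X1 ~ Bin(18, p) and X2 ~ Bin(19, p). The chance of going on past the lower stop and ending with at least 14 of 37 is Σ(a ≥ 6) P(X1 = a) · P(X2 ≥ 14 − a). This is 0.0496 at p = 0.25 and 0.806 at p = 0.45, which matches 5% and 80%.

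**2. Wilson limits.** With p̂ = x/n, the limits are [p̂ + z²/2n ± z√(p̂(1 − p̂)/n + z²/4n²)] / (1 + z²/n), where z = 1.2816 for 80%. For the largest count that stops the trial, 5/18:
- p̂ = 0.2778, z²/2n = 0.0456, 1 + z²/n = 1.0912, and the ± term is 0.1428.
- The limits are (0.3234 ± 0.1428)/1.0912 = 16.6% to 42.7%.

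Every futility stop therefore gives an 80% interval that lies wholly below 45%. At n = 37, 12 responses give an upper limit of 42.9% and 21 give a lower limit of 46.3%, so 12 or fewer miss low and 21 or more miss high.

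**3. Coverage of the 80% interval at 45%.** All outcomes are enumerated and the probabilities summed:
- Too low: 14.8%. Of this, 10.8% is the futility stop, which leaves 14.8 − 10.8 = 4.0% from completed trials.
- Too high: 10.2%.
- Coverage: 100 − 14.8 − 10.2 = 75.0%.

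The same interval with 37 fixed covers 81.4%, so the loss of about 6 points comes from the stopping rule and not from discreteness at 37. Dropping the upper stop leaves 75.0%. Analysing 18 + 23 = 41 gives 73.2%.

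**4. Other true rates and the 95% interval.** The 80% two-stage coverage is 83.4% at 30%, 79.7% at 35%, 78.1% at 40%, 68.1% at 43% and 79.1% at 50%. The average over 25–50% is about 78%, against about 80% with 37 fixed. The 95% interval covers 95.6% at 45% and averages about 95% over 25–50%, with a minimum of 91.8%.

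**5. Given entry to stage 2.** At 45%, about 89.1% of trials go on, and all the covering outcomes lie there: 75.0/89.1 = 84.2%.

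**6. Bias, in percentage points.** For x responses in 37, the two-stage unbiased estimate (UMVUE) is Σ (a/18)·C(18,a)·C(19,x−a) / Σ C(18,a)·C(19,x−a), summed over stage 1 counts a = 6 to 14. For a trial stopped at stage 1 it is x/18.

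| True ORR | Raw, overall | Raw, given stage 2 | UMVUE, given stage 2 |
|---|---|---|---|
| 25% | -1.8 | +6.2 | +12.7 |
| 30% | -2.2 | +4.6 | +9.4 |
| 35% | -2.2 | +3.2 | +6.5 |
| 40% | -1.7 | +2.0 | +4.2 |
| 45% | -1.1 | +1.2 | +2.4 |

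Overall, the UMVUE has zero bias at every rate checked. At 14/37 the raw ORR is 37.8% and the UMVUE 40.6%; at 13/37 they are 35.1% and 39.1%.

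**7. A two-stage interval.** Order the outcomes as futility stops, then completed trials by count, then early high stops, and invert mid-p tail probabilities. At 45% this covers 79.0% for nominal 80% and 96.1% for nominal 95%. The gain is 79.0 − 75.0 = 4.0 points, which equals the low misses among completed trials. Futility stops still miss 45%: at 5/18 the mid-p upper limit is 43.0%. At 14/37 the 80% limits are 28.6% to 49.8%, against Wilson's 28.3% to 48.4%. The version without mid-p is conservative, at 90.4% for nominal 80%.

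**The case against.** The strongest case against has four parts.

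- **One point on an oscillating curve.** Coverage is above 80% at 30% and close to it at 35% and 50%, and a fixed sample of 37 also oscillates. This stands as a limit on size: the average loss is about 2 points. It does not remove the loss at 45%, where the fixed-sample interval holds its level.
- **Completed trials are well covered.** At 45%, futility stops supply 10.8 of the 14.8 points of low misses, and given stage 2 the coverage is 84.2%. That is correct for that rate. The design's alpha and power are, however, defined over stopped and completed trials together, so the unconditional figure is the natural one for the interval too.
- **The 95% interval holds.** The only comparator interval quoted in section 11.1 is a 95% one, so a comparison of 95% limits is hardly affected. This stands.
- **The unbiased estimate is no plain improvement.** A reader might infer that the UMVUE should replace the raw proportion as the headline ORR. The figures do not support that. It is unbiased only when stopped and completed trials are averaged. Given stage 2, the case most likely to be compared with other studies, its upward bias is about double. Its root mean squared error is also larger at 25–35% (9.9 v 8.4 points at 25%) and smaller only from about 40% (9.3 v 9.95 at 45%). Preferring it is a trade-off.

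An SAP could also add an adjusted interval beside Wilson without contradicting the protocol. As written, though, the protocol's only stated intervals are the unadjusted ones.

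**Conclusion.** The point holds for the 80% interval. Section 11.3 attaches a fixed-sample method to a design whose size depends on the data, and the nominal 80% limits cover 75.0% at the planning value, about 68% at worst near 43%, and about 78% on average over 25–50%.

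A reader might go further and infer that 75% is typical, that the reported ORR is seriously distorted, or that the trial's decision is unsafe. None of these follows. The average shortfall is about 2 points, the 95% interval is near nominal, the overall bias of the raw proportion is at most 2.2 points over 25–45%, and the stage sizes still deliver the stated alpha and power.

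The figures assume an analysis of exactly 18 or 37 patients, 15 of 18 read as at least 15, and no over-run while the 6-month responses of the first 18 mature. The protocol leaves room for departures: it recruits 41, replaces non-evaluable patients (section 11.6) and calls for an intention-to-treat analysis (section 11.2). Such departures would change the exact numbers, as the 73.2% for 18 + 23 shows.

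**What to change.** In section 11.3, report 80% and 95% intervals for the ORR that respect the stage 1 stopping rule, for example two-stage sample-space ordering with mid-p. Base them on the stage sizes actually analysed. Label the Wilson limits as unadjusted for the two-stage design.

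Keep the raw proportion as the reported ORR. Add the two-stage UMVUE beside it as a supplementary estimate. State that it is unbiased only when averaged over stopped and completed trials, and that given entry to stage 2 its upward bias is about double that of the raw proportion.

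The cost is one more interval and one more estimate to report and explain, and a little more code, including handling of stage sizes that differ from plan. No further patients or data are needed.

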# 11.4 Secondary endpoints

- ORR and DCR at 12m and 24m reported with 80% and 95% CI
- Progression-free survival
  - Progression free survival will be calculated from the date of registration until clinically or radiologically documented disease progression or death from any cause, whichever comes earlier.
  - Patients free from a progression event will be censored on the date of last follow up.
  - A progression-free survival curve will be generated using the methods of Kaplan and Meier. All patients registered in the study will be included. Median PFS rate will be reported with 80% and 95% CI.
  - Duration of response as measured by Kaplan-Meier at each follow-up, or until progression, will be reported.

#### Overall survival

 An overall survival curve will be generated using the methods of Kaplan and Meier. The median overall survival will be reported with 80% and 95% CI.

#### Toxicity

 The proportion of patients experiencing grade 3 or 4 toxicity as measured by NCI-CTCAE v5.0 whilst on treatment. The number of SAEs will be reported.

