# 2.3 Secondary endpoints

- To evaluate safety and tolerability including the frequency, severity and relatedness of AEs to the study treatment. AEs will be assessed according to CTCAE v5.0.
- To assess ORR at 12 months and 24 months.
- To assess disease control rate (DCR) at 6, 12 and 24 months. DCR is ORR plus stable disease (SD).
- To assess progression-free survival (PFS) defined as the time from registration to the first of one of the following: development of clinical/radiological disease progression (composite criteria/ RECIST 1.1) or death from any cause.
- To assess overall survival (OS) defined as time from registration to the date of death from any cause.
- To assess patient health status and quality of life (QoL) using the patient reported outcome measures EQ-5D-5L, EORTC QLQ-C30, Skindex-16, FNAE and the Hornheide questionnaire.
- To estimate the time to response (TTR: defined as the time from the start of treatment to the first objective tumour response (tumour shrinkage of ≥30%)) and duration of response (DOR: the time from response to progression/death) to cemiplimab.

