# 6.2 **On-treatment** assessments (within 7 days prior to cycle 1 and then within 5 days prior to each subsequent cycle of treatment)

Patients will be seen and assessed prior to each cycle of treatment. Please refer to Appendix 6 for contingency measures during extenuating circumstances. Assessment should include:

- Limited symptom-directed physical examination including vital signs (weight, blood pressure, heart rate, oxygen saturation and temperature).
- ECOG performance status.
- Full blood count, U+Es (including urea, sodium, potassium, total calcium and creatinine), liver function tests (to include ALP, ALT, Albumin and Bilirubin) and LDH. Thyroid function tests (including TSH, T4 and if required T3), cortisol and glucose (random) to be performed at each pre-assessment up to and including cycle 5 then every other cycle.
- Serum pregnancy test if required

- Estimated GFR to be assessed according to local practice (preferred technique of eGFR using the CKD-EPI formula (see Appendix 3)).
- Toxicity assessment (CTCAE v5.0) from day 1 of treatment up to and including 95 days after the last trial treatment.
- Updated recording of concomitant medication use, with relevant dates.
- Photography of skin lesion(s), including those being followed as target lesions. To be performed 12 weeks (+/- 7 days) after cycle 1 day 1 and before cycle 5. Subsequent photography will be taken every 12 weeks (+/- 7 days) from the previous photography whilst patient is on treatment. NB Target lesions need to be measured in both the longest diameter and the perpendicular diameter.
- MRI/CT scan (with contrast) only if being used to follow target lesions. Use the same modality and scan the same areas as in the baseline scan. Scan 1 to be performed 12 weeks (+/- 7 days) after cycle 1 day 1 and before cycle 5. Subsequent scans will then be performed every 12 weeks (+/- 7 days) from the previous scan whilst patient is on treatment.
- Completion of Quality of life questionnaires EQ-5D-5L, EORTC QLQ-C30, Skindex-16, FNAE and the Hornheide questionnaire at pre cycle 5, 9, 13, 17, 21, 25, 29, 33, and end of treatment visits.

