#### 6.5.2 Quality of Life

The EQ-5D-5L, EORTC QLQ-C30, Skindex-16, FNAE and the Hornheide questionnaire questionnaires will be used in this trial to assess quality of life whilst the patient is on treatment. These should be completed at baseline and then at the pre-cycle assessment visits for cycle 5, 9, 13, 17, 21, 25, 29, 33 and end of treatment visit.

Please refer to Appendix 6 for contingency measures during extenuating circumstances.

6.6	Visit schedule

Trial Evaluation	Baseline	cycle 1	cycle 1 cycle 2	cycle 3	cycle 4	cycles 5-34	End of treatment	Months following completion of treatment visit 					
								3	6	9	12	18	24
	Within 7 days of registration	Within 7 days pre treatment	Within 5 days pre treatment	Within 5 days pre treatment	Within 5 days pre treatment	Within 5 days pre treatment	Within 6 weeks of day 1 of last treatment cycle						
Physical exam¹	Х	Х	Х	Х	Х	Х	X	Х	Х	Х	Х		
ECOG	Х	Х	Х	Х	Х	Х	X	Х	Х	Х	Х		
Vital signs and observations	Х	Х	Х	Х	Х	Х	Х	Х	Х	Х	Х		
12 lead ECG	Х												
Medical & cancer history	Х												
Haematology & biochemistry  including serum pregnancy test if required and eGFR assessment.	Х	Х	Х	Х	Х	Х	Х	Х					
Thyroid function tests 	Х	Х	Х	Х	Х	X 	Х	Х					
Serology - Viral screen (HIV, Hep B and Hep C)	Х												
Concomitant medications	Х	Х	Х	Х	Х	Х	Х	Х					
Adverse Events 	Х	Х	Х	Х	Х	Х	Х	Х					
Photography and MRI/CT scan of area encompassing the primary lesion)	Xe				X 	X8	Χ 	X8	X8	X8	X8		
Administration of cemiplimab 		Х	Х	Х	Х	Х							 
Quality of life questionnaire - EQ- 5D-5L, EORTC QLQ-C30, Skindex-16, FNAE and the Hornheide questionnaire	Х					X 	Х						
Survival and anti-cancer therapy								Χ	Χ	Χ	Χ	Х	Χ

- 1. Full physical examination to be carried out at baseline. All subsequent visits a limited physical examination to be performed.
- 2. Full blood count; urea, sodium, potassium, total calcium, creatinine (U&Es), ALP, ALT, Albumin, Bilirubin (LTFs) and LDH.
- 3. Thyroid function tests (TSH, T4 and T3), cortisol and glucose (random).
- 4. Thyroid function tests to be performed at cycle 5 and then every other cycle whilst on treatment.
- 5. To be collected from day 1 of treatment until 95 days from day 1 of the final treatment cycle. Any AEs that are ongoing at this time point will be followed to resolution.
- 6. Within 6 weeks prior to commencing first cycle of cemiplimab

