#### 8 SAFETY AND PHARMACOVIGILANCE

#### 8.1 **Definitions**

#### 8.1.1 Adverse Events (AEs)

An adverse event is any untoward medical occurrence in a patient administered a drug; the event does not necessarily have a causal relationship with the treatment or usage.

The following should not be recorded as AEs if recorded as medical history/concomitant illness on the CRF at screening:

- Pre-planned procedure, unless the condition for which the procedure was planned has worsened from the first trial related activity after the subject has signed the informed consent.
- Pre-existing conditions found as a result of screening procedures unless the condition worsens from the first trial related activity after the subject has signed the informed consent.

Procedure for collecting Adverse Events

- For the purpose of this trial, any detrimental change in the patient's condition that
  occurs after the subject has started trial treatment, up to and including 95 days
  after last trial treatment should be considered an AE.
- All AEs regardless of their seriousness or relationship to the product should be recorded on the relevant Case Report Form (eCRF) from day 1 of treatment until 95 days after last treatment date. Investigator's assessment of the seriousness and causal relationship between the AE and the study medication should also be provided on the eCRF. AEs will continue to be followed until resolution or patient comes off trial.
- Whenever one or more signs and/or symptoms correspond to a disease or a welldefined syndrome only the main disease/syndrome should be reported. The severity of adverse events will be graded according to the NCI-CTC criteria (CTCAE v5.0).

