#### 9 END OF TREATMENT (EOT)

End of treatment for a patient is defined as no later than 6 weeks after the first day of the last treatment cycle. The reason for treatment discontinuation will be documented on the appropriate CRF.

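### The protocol's only patient-level toxicity rate leaves out grade 5 events and, on its natural reading, severe events arising after treatment stops

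*Protocol*

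**What the plan says.** The Toxicity item of section 11.4 names two summaries. The first is a rate: "The proportion of patients experiencing grade 3 or 4 toxicity as measured by NCI-CTCAE v5.0 whilst on treatment". The second is a count: "The number of SAEs will be reported". Section 11 gives no other safety summary.

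The endpoint behind them, in section 2.3, is "To evaluate safety and tolerability including the frequency, severity and relatedness of AEs to the study treatment". It sets no limit on grade or period.

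Collection is equally broad. Under section 8.1.1, adverse events, whatever their seriousness or relationship to the product, are recorded "from day 1 of treatment until 95 days after last treatment date". Section 6.2 prescribes "Toxicity assessment (CTCAE v5.0) from day 1 of treatment up to and including 95 days after the last trial treatment". Footnote 5 of the visit schedule (section 6.6) gives the same length, counted from the start of the final cycle: "To be collected from day 1 of treatment until 95 days from day 1 of the final treatment cycle".

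Section 9 bounds the treatment period: "End of treatment for a patient is defined as no later than 6 weeks after the first day of the last treatment cycle". Section 6.3 places the end-of-treatment visit 3 to 6 weeks after the first day of the final cycle.

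**The concern.** The rate carries two restrictions that neither the endpoint nor the data collection has.

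- **Grade.** CTCAE grade 5 is a fatal event. A rate confined to grades 3 and 4 does not count a patient whose only severe toxicity was fatal.
- **Period.** A rate confined to time on treatment stops before collection does. A first severe event between the end of treatment and day 95 is collected and graded but not counted.

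Both restrictions shrink the numerator and leave the denominator alone, so they can only lower the rate. Tolerability is part of the hypothesis in section 2.1, and section 7.5 warns that immune-related events can be more severe than those of other drug classes. The period restriction also bears unevenly on patients. Section 7.5.4 ends treatment for several kinds of toxicity, and those who stop early have the largest part of their observation outside the rate.

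**Working it through.** The protocol states no expected toxicity rate, so there is no figure to reproduce. The check measures how much of the collected window the rate leaves out and what each omitted patient is worth.

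**Inputs**
- Collection ends 95 days after the last dose (section 8.1.1).
- Cycle length is 21 days, with dosing on day 1 (section 7.1).
- Treatment ends at the latest 42 days after day 1 of the last cycle (section 9).
- The maximum is 34 cycles (trial summary).
- 41 patients are to be recruited, 37 of them evaluable (section 4.2).

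The protocol does not say when the on-treatment period ends. Two cut-offs after the last dose are used: day 21 (end of the last cycle) and day 42 (latest end of treatment). They match the 3-to-6-week window of the end-of-treatment visit.

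**Days left out**
- Cut-off at day 42: 95 − 42 = 53 days.
- Cut-off at day 21: 95 − 21 = 74 days.

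**Share of a patient's collection window left out**

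With *c* cycles given on schedule, the window is (*c* − 1) × 21 + 95 days.

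| Cycles | Window (days) | Left out, day-42 cut-off | Left out, day-21 cut-off |
|---|---|---|---|
| 1 | 0 + 95 = 95 | 53/95 = 56% | 74/95 = 78% |
| 4 | 63 + 95 = 158 | 53/158 = 34% | 74/158 = 47% |
| 34 | 693 + 95 = 788 | 53/788 = 7% | 74/788 = 9% |

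**Effect per omitted patient**
- 1/41 = 2.4 percentage points.
- 1/37 = 2.7 percentage points.

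**Illustration with assumed counts.** Suppose 8 of 41 patients have a grade 3 or 4 event on treatment: 19.5% (95% Wilson interval 10.2 to 34.0). If two more have only a fatal or only a post-treatment severe event, the rate over grades 3 to 5 and the full window is 10/41 = 24.4% (13.8 to 39.3). The counts 8 and 2 are not from the protocol.

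**Which summary captures which event**

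| Patient's only severe event | Rate in section 11.4 | Serious event count |
|---|---|---|
| Grade 3–4, on treatment | Yes | If serious |
| Grade 5 | No | Yes, as an event, to day 95 |
| Grade 3–4, after treatment, serious | No, on the narrow reading | Yes, as an event |
| Grade 3–4, after treatment, not serious | No, on the narrow reading | No |

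**The case against.** A reader might infer that the safety analysis as a whole ignores deaths and late events. The protocol does not support that. Section 11.4 also reports the number of serious adverse events. Section 8.1.2 defines these to include events resulting in death, up to 95 days after the last dose. Section 8.4 requires related serious events to be reported even later, and deaths from any cause enter progression-free and overall survival. This limits the point to the rate, but it does not repair the rate: a count of events cannot be turned into a proportion of patients, and non-serious late events of grade 3 or 4 fall outside it.

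The on-treatment period is undefined, and section 6.2, whose heading concerns on-treatment assessments, itself runs toxicity assessment to day 95. On that wider reading the period restriction disappears. So the period half of the point is an ambiguity with a natural narrow reading, not an established exclusion. The grade half does not depend on it.

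A reader might also infer that every patient who dies of toxicity is counted as free of severe toxicity. That is too strong, because a patient with a separately recorded grade 3 or 4 event on treatment before death is already in the numerator. Nor is the one-cycle, day-21 figure typical: for a full course the share left out is 7–9%.

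Full adverse event tables are commonly left to the statistical analysis plan, and their absence here is no fault. The difficulty is that the protocol does fix a rate, and fixes it more narrowly than its own endpoint. An analysis plan that follows section 11.4 inherits the gap, and one that widens the rate departs from the protocol.

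Finally, no decision rule uses this rate. Sample size and interim stopping rest on response (section 11.1), and the data monitoring committee oversees safety. That stands, and it keeps the point moderate.

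**Conclusion.** The point holds for the toxicity rate, not for safety reporting as a whole. As worded, the rate omits patients whose only severe event is grade 5. Unless the on-treatment period is taken to run to day 95, it also omits those whose only severe event arises after treatment stops.

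The direction is certain: the rate can only be too low. Its size cannot be derived, because the protocol gives no expected number of such patients. The window shares in the working assume dosing on schedule and an on-treatment period ending 21 to 42 days after the last dose. The 2.4 points per patient assume all 41 recruited patients form the denominator. The loss is small for patients who complete treatment and largest for those who stop early. The change should be made, but it does not threaten the trial's main conclusion.

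**What to change.** Replace the rate in the Toxicity item of section 11.4 with: *the proportion of patients with at least one adverse event of grade 3 or higher (grades 3 to 5, CTCAE v5.0), overall and treatment-related, from first dose to 95 days after the last dose.* Add that fatal adverse events are reported separately. Keep the serious adverse event count. An on-treatment rate may be shown as a supplement, provided the end of that period is defined.

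The cost is about one sentence. All the data are already collected and graded, and neither the sample size nor the stopping rule is affected. The reported rate may come out slightly higher.
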